24.3 Demographics

The following baseline values and patient characteristics will be summarized descriptively in order to describe the study population: age, gender and ethnic origin.

24.4 Analysis of efficacy

Primary endpoint:

Colonic geometric center at 24 h as measured by scintigraphy, as compared to placebo.

Secondary endpoints:

- 1. Colonic filling at 6 h measured by scintigraphy, as compared to placebo.
- 2. $T_{1/2}$ of ascending colon emptying measured by scintigraphy, as compared to placebo.
- 3. Colonic geometric center at 48 h measured by scintigraphy, as compared to placebo.
- 4. $T_{1/2}$ of gastric emptying of solids
- 5. Assess the effects on stool frequency and consistency based on the Bowel Pattern Diary and treatment effects on symptom responses specific to constipation, overall and for active treatment compared to placebo.
- 6. Evaluate the pharmacokinetic (PK) characteristics for each dose of A3309.
- 7. Assess the safety and tolerability of A3309 administered as an oral tablet.

24.5 Transit data analysis

A variable region of interest program is used to quantitate the counts in the stomach and each of four colonic regions: ascending, transverse, descending, and combined sigmoid and rectum. These counts were corrected for isotope decay, tissue attenuation, and downscatter of ¹¹¹ In counts in the ^{99m}Tc window.

Data will be analyzed as in previous studies.

1. Geometric mean of counts in anterior and posterior gastric regions of interest will be used to estimate by power exponential analysis of the proportionate emptying over time of counts from ^{99m}Tc solids and ¹¹¹In from the stomach. The proportion of ^{99m}Tc and ¹¹¹In reaching

the colon at 6 hours will also be estimated as a measure of orocecal (and a surrogate for small bowel) transit.

- 2. Geometric center of colonic counts for solids at 4, 24 and 48 hours will be estimated using geometric mean of counts in ascending, transverse, descending and rectosigmoid colon and stool (weighted by factors of 1 to 5 respectively). The primary variable of interest in overall colonic transit is the geometric center at 24 hours.
- 3. Ascending colon emptying t1/2 will be estimated by power exponential analysis of the proportionate emptying over time of counts from the colon. The primary data for this analysis will be the proportion of decay and depth-corrected counts in the ascending colon on the hourly scans on the first day of transit measurement and the 24 h data.

The primary summaries obtained for comparison of transit profiles will be the colonic geometric center at 24 hours and the ascending colon emptying $t\frac{1}{2}$. The geometric center is the weighted average of counts in the different colonic regions: ascending (AC), transverse (TC), descending (DC), rectosigmoid (RS), and stool. At any time, the portion of colonic counts in each colonic region is multiplied by its weighting factors as follows: (%AC x 1 + %TC x 2 + %DC x 3 + %RS x 4 + %stool x 5)/100 = geometric center. Thus, a high geometric center implies faster colonic transit. A geometric center of 1 implies that all isotope is in the ascending colon and a geometric center of 5 implies that all isotope is in the stool. The $t\frac{1}{2}$ of ascending colon emptying is also estimated by plotting the activity-time curve for percent residing in the ascending colon; linear interpolation is used to connect points.

24.6 Stool frequency and stool consistency

Patients are asked to keep a daily bowel pattern diary documenting the number of stools and the consistency (Bristol Stool Scale (28)) of each stool. These are averaged as number of bowel movements or consistency of bowel movements per day per patient. Number of bowel movements and consistency are subsequently averaged over the study periods (i.e. run-in and treatment) per patient. The ANCOVA will be used to assess treatment effects on each of these two measures separately, using the corresponding run-in values as covariates. In addition, treatment effects on specific constipation symptoms, considered as discrete categorical responses, will be evaluated by a contingency table analysis of the post-treatment responses based on the final post-treatment bowel pattern diaries and questionnaires concerning constipation symptoms and treatment efficacy.

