4 ABBREVIATIONS AND TERMS

Abbreviation/Term	Definition	
A3309	Investigative drug substance code	
A3309- ¹⁴ C	Carbon-labeled drug substance	
AE	Adverse event	
ALT	Alanine aminotransferase	
ANCOVA	Analysis of covariance	
ANOVA	Analysis of variance	
AP	Alkaline phosphatase	
aPPT	Activated partial thromboplastin time	
AST	Aspartate aminotransferase	
BM	Bowel movement: A single defecation event with a beginning and end (as interpreted by the patient), which may include single or multiple stools.	
BMI	Body mass index	
bp	Blood pressure	
C4	7α-hydroxy-4-cholesten-3-one	
CIC	Chronic idiopathic constipation	
C_{max}	Maximum plasma concentration observed post-dose	
CRO	Contract research organization	
CSBM	Complete spontaneous bowel movement: A spontaneous bowel movement that is accompanied by the patient reporting a feeling of complete evacuation.	
CV	Cardiovascular	
CYP_{450}	Cytochrome P ₄₅₀	
ECG	Electrocardiogram	
GCP	Good Clinical Practice	
GI	Gastrointestinal	
HbA _{1c}	Glycosylated hemoglobin	
IB	Investigator's Brochure	
IBAT	Ileal bile acid transporter	
IBS	Irritable bowel syndrome	
IC ₅₀	Concentration for 50% inhibition of the effect	
ICF	Informed consent form	

Abbreviation/Term	Definition
IRB	Institutional Review Board
ITT	Intent to treat analysis
i.v.	Intravenous
LDL-C	Low density lipoprotein cholesterol
NOAEL	No observed adverse effect level
NOEL	No observed effect level
PD	Pharmacodynamic
PK	Pharmacokinetic
SAE	Serious adverse event
SBM	Spontaneous bowel movement: A bowel movement that occurs in the absence of a laxative/enema use or manual disimpaction. For the purpose of this protocol, bowel movements that occur within 24 hours of laxative/enema use will not be considered spontaneous bowel movements.
SAP	Statistical Analysis Plan
$t_{1/2}$	Half-life
t_{max}	Time to maximum observed plasma concentration

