13 INCLUSION CRITERIA

- 1. Females aged 18 to 65 years old inclusive
- 2. An adaption of Rome II criteria for functional constipation will be used. Eligible patients must have functional constipation for the previous three months with symptom onset at least six months prior to diagnosis with less than three complete spontaneous bowel movements per week with two or more of the following:
 - a. hard or lumpy stools at least 25 % of the time
 - b. straining during a bowel movement at least 25 % of the time
 - c. sensation of incomplete evacuation at least 25 % of the time
 - d. sensation of anorectal obstruction/blockage at least 25 % of the time
- 3. A normal rectal exam result on file within the past 2 years or performed at Visit 1 screen by a qualified gastroenterologist to exclude the possibility of an evacuation disorder. Examination must exclude findings suggestive of an evacuation disorder such as high sphincter tone at rest, failure of perineal descent and spasm, tenderness or paradoxical contraction of the puborectalis muscles.
- 4. Females of child-bearing potential (those who have not experienced a bilateral tubal ligation, hysterectomy or menopause) must use an acceptable method of contraception during the study. Acceptable methods are surgical sterilization, hormonal methods such as oral contraceptives, Norplant and Depo-Provera, double barrier method such as a condom and spermicide, and an IUD. Abstinent females may participate if they agree to use the double barrier method should they become sexually active during the study.
- 5. Able to provide written informed consent prior to any study procedures being performed

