16 RESTRICTIONS

Patients must report to Charlton 7 CRU fasting for the previous eight hours for all study visits, Visits 1 to 7.

Rescue medications (Milk of Magnesia, Dulcolax and Fleets/tap water enemas) may be used but only under the direction of the PI. Rescue medications must not be used within the seven days prior to both the abbreviated and full transit scintigraphy tests. Since each patient's schedule will differ, each patient will be instructed as to when rescue medication may not be taken.

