34.5 Patient bowel pattern diary

Daily Diary	Date				
Please record the time the	ne study medication	n was taken:_	am		
If you had no bowel mov	ements today, plea	se check this box:	no bowel mo	vement today	
	Describe the consistency of bowel movement	Describe the ease of passage of bowel movement	How much did you strain during the bowel movement?	Did you feel like you completely emptied your bowels?	Did you feel like you had a sensation of obstruction and/or blockage during the bowel movement?
	1 Hard lumps 2 Lumpy sausage 3 Cracked sausage 4 Smooth sausage 5 Soft lumps 6 Mushy 7 watery	1 Manual Disimpaction 2 Enema needed 3 Straining needed 4 Normal 5 Urgent wopain 6 Urgent w/pain 7 Incontinent	 Not al all A little bit More straining than not A great deal An extreme amount 	1 No 2 Yes	1 No 2 Yes
1 am hr. min pm					
2 am hr. min pm					
3 am hr. min pm					
4 am hr. min pm					
5 am hr. min pm					
6 am hr. min pm					
7 am hr. min pm					
8 am hr. min pm					
Have you had any unusual	events today?	No 🗌	Yes (complete be	elow)	
Event		loderate / Severe	Resolved / Ongoin		
Event		loderate / Severe loderate / Severe	Resolved / Ongoin Resolved / Ongoin	-	
Have you taken any atypica	Il medications toda	v? No □	Yes (complete be	elow)	
Medication		cation	Medicati		
Dose		Dose		ese	
Time(s)	Ti	me(s)	Time	(s)	

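### Stool frequency and consistency are averaged over all bowel movements, including any produced by permitted rescue, although the protocol defines spontaneous movements and selects patients on them

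*Combined protocol and SAP*

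**What the plan says.** Section 24.6 takes the daily number and consistency of bowel movements from the diary and averages each over run-in and treatment: "These are averaged as number of bowel movements or consistency of bowel movements per day per patient". The model follows: "The ANCOVA will be used to assess treatment effects on each of these two measures separately, using the corresponding run-in values as covariates". Section 24.1 adds mean ease of passage to the diary summaries. None of these carries a spontaneous or rescue-free qualifier.

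Section 4 defines a bowel movement as "A single defecation event with a beginning and end (as interpreted by the patient), which may include single or multiple stools", which takes in movements caused by rescue. It then defines SBM as a movement without laxative, enema or manual disimpaction, and adds: "For the purpose of this protocol, bowel movements that occur within 24 hours of laxative/enema use will not be considered spontaneous bowel movements". A CSBM is an SBM with a feeling of complete evacuation. Section 13 selects patients on "less than three complete spontaneous bowel movements per week". SBM and CSBM are absent from the endpoint lists (Sections 9 and 24.4) and from the analysis (Sections 24.1 and 24.6).

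Section 16 permits Milk of Magnesia, Dulcolax and enemas under the principal investigator's direction, with one limit: "Rescue medications must not be used within the seven days prior to both the abbreviated and full transit scintigraphy tests". Section 20.3 permits rescue at the investigator's discretion and does not repeat that limit.

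**The concern.** Patients are selected on one quantity and evaluated on another. Under Section 24.6, a movement brought on by a laxative or enema counts as a response to study drug or placebo, and its form and ease score enter the patient's means. If the arms use rescue to different extents, part of the estimated difference reflects rescue rather than A3309. With 12 patients per arm, a few rescued patients can move a mean.

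Comparability also suffers. Section 8.8 reports that the earlier patient study, A3309-001, had complete spontaneous movements as a secondary objective and cites the change in SBMs to Week 1 as a sign of effect. The all-movement count planned here is not the same measure.

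**Working it through.** **Plan's own figure.** There is none to reproduce. Table 6 in Section 24.9 covers only gastric emptying and the 24-hour geometric center. The documents give no stool-frequency SD, expected stool effect or rescue rate.

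**Where rescue can fall**
- Treatment lasts 14 days and the full transit test starts on day 12 (Section 10). The seven days before it are days 5-11.
- Days 1-4 are open: 4/14 = 29% of treatment days.
- Days 12-14, during the test, are not expressly barred. Counting them gives 7/14 = 50%.
- Visit 2 is 7-14 days after Visit 1 and its last seven days are barred, so 0-7 early run-in days are open. Visit 3 follows Visit 2 by 0-3 days, which are also open (Section 11.2).

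**Size of the shift (all inputs assumed)**
- Rescue users, placebo/active: 25%/5% (low) to 75%/20% (high).
- One use every other open day, so 2 uses in 4 open days.
- 1.5 extra stools per use.

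Shift per day = (placebo share − active share) × uses × stools per use / 14.
- Low: (0.25 − 0.05) × 2 × 1.5 / 14 = 0.043 per day; × 7 = 0.3 per week.
- High: (0.75 − 0.20) × 2 × 1.5 / 14 = 0.118 per day; × 7 = 0.8 per week.

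**Dependence on direction.** Let D be the true SBM difference per day, r the placebo excess of rescue movements per open day, and f the open fraction. Proportional attenuation is r × f / D. With an assumed D = 0.5 and f = 4/14:

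| r | Change in the estimated difference |
|---|---|
| 0 (equal use) | none |
| 0.1 | shrinks by 6% |
| 0.25 | shrinks by 14% |
| 0.5 | shrinks by 29% |
| −0.25 (more on active) | grows by 14% |

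The sign follows the imbalance, and the documents do not say what the imbalance will be.

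**Can SBM and CSBM be derived?** The diary (Section 34.5) has a clock time for each movement, ease codes 1 and 2 for disimpaction and enema, a medication field with dose and time, and the item "Did you feel like you completely emptied your bowels". Section 20.3 requires all concomitant therapy in the CRF. These are sufficient, provided rescue is recorded.

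**The case against.** The strongest reply is that the exposure is small and the outcome secondary. The primary endpoint is scintigraphic. The seven-day bar removes half the treatment period, rescue needs the investigator's direction, and Section 14 excludes patients taking osmotic or stimulant laxatives. The high case above has nine of 12 placebo patients (75%) using rescue twice in four days, which is extreme. It also treats every rescue stool as extra, although some would replace a stool that was coming anyway. All of this stands as a limit on size. It does not supply the missing rule.

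The SBM measure has its own fault. Dropping every stool within 24 hours of rescue while dividing by all days also removes stools that might have occurred anyway. If placebo patients use more rescue, that tilts slightly toward active drug. The diary has no dedicated rescue item either: it asks about atypical medications, which a habitual laxative user may leave blank, and ease codes 1 and 2 do not identify oral laxatives. Both points stand as small downsides and are reasons to keep the all-stool analysis and report rescue use.

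The synopsis defers exploratory efficacy analyses to a SAP, but no SBM rule appears in the text available.

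**Conclusion.** The concern holds as a gap in the definition of a secondary outcome. Section 24.6 counts rescue-induced stools as response and leaves the protocol's own SBM definition unused. This can bias the comparison if rescue use differs by arm, and otherwise mainly adds noise. The 0.3 to 0.8 stools per week rests wholly on the assumed shares, frequency and stools per use.

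Four stronger readings are tempting but not supported:
- *That the plan biases the result toward no effect.* This needs more rescue on placebo. It is plausible if the drug works, but no rescue use by arm is given.
- *That the shift reaches 0.5 to 1.4 per week.* Seven open days give 0.20 × 3.5 × 1.5 / 14 = 0.075 and 0.55 × 3.5 × 1.5 / 14 = 0.206 per day. This requires repeated rescue during the transit test itself, which the wording leaves open but nothing in the documents suggests.
- *That the shift is large against the entry limit of three per week.* That limit counts CSBMs, a subset of all movements, so the scales differ.
- *That rescue in the run-in biases the comparison.* The run-in precedes randomization. A contaminated baseline covariate costs precision and does not systematically favour an arm.

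**What to change.** In Section 24.6:
- Make SBM per day the stool-frequency measure, using Section 4's 24-hour laxative/enema rule and excluding manual disimpaction. State the denominator.
- Average consistency and ease of passage over SBMs, and add CSBM per week.
- Apply the same rule to run-in and treatment.
- Identify rescue from diary medication entries, ease codes 1 and 2, and CRF concomitant therapy.
- Report rescue use by arm and period, which will show whether an imbalance exists and in which direction.
- Keep the all-stool analysis as a sensitivity.

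Sections 16 and 20.3 should also be reconciled on when rescue is allowed, including days 12-14. This point takes no view on what that rule should be.

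The cost is a derivation from fields already collected, with no new data or visits. Two consequences should be stated in advance. Ease codes 1 and 2 drop out of an SBM-only mean by construction. A patient with no SBM in a period has a frequency of zero but no consistency or ease mean, so the plan should say how she is handled.

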9 STUDY AIMS AND ENDPOINTS

9.1 Aim

To assess the dose related effects of A3309 on small bowel and overall colonic transit and bowel function in patients with functional constipation.

9.2 Primary endpoint:

Colonic geometric center at 24 h as measured by scintigraphy, as compared to placebo.

9.3 Secondary endpoints:

- 1. Colonic filling at 6 h measured by scintigraphy, as compared to placebo.
- 2. $T_{1/2}$ of ascending colon emptying measured by scintigraphy, as compared to placebo.
- 3. Colonic geometric center at 48 h measured by scintigraphy, as compared to placebo.
- 4. $T_{1/2}$ of gastric emptying of solid
- 5. Assess the effects on stool frequency and consistency based on the Bowel Pattern Diary and effects on symptom parameters coupled to constipation as well as the overall treatment effect, as compared to placebo based on a six question survey given at the end of the pre-treatment period and the post-treatment period.
- 6. Evaluate the pharmacokinetic (PK) characteristics and pharmacodynamic effects for each dose A3309.
- 7. Symptoms of constipation

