11.3 Schedule of Visits

Visit 1 Study Entry

Potential study patients will arrive at the Charlton 7 CRU fasting for the previous eight hours. Patients will be required to sign the ICF after review and explanation of the study and after all questions have been answered. Inclusion and exclusion criteria will be accurately reviewed.

After reviewing and signing a patient ICF, they will have a brief interview (including demographics, medical history and current medications) and a physical examination performed by a study physician. If the results of a normal rectal examination to exclude the possibility of an evacuation disorder are not documented within the previous two years by a qualified gastroenterologist, this exam will be performed

⁴ Laboratory safety assessments include clinical chemistry (ALT; Albumin; Alkaline phosphatase; AST; Bilirubin, total; Calcium; Chloride; C-Reactive Protein; Creatinine; GGT; Glucose; Potassium; Protein, total; Sodium; Urea; Uric acid), hematology (hemoglobin; hematocrit; MCV; platelet count; RBC count; WBC count with differential), coagulation studies (Activated partial prothrombin time aPPT; Prothrombin time PT), urinalysis (blood; glucose; ketones; leukocytes; nitrites; pH; protein), drugs of abuse urine screen (alcohol; amphetamines; barbiturates; benzodiazepines; cocaine; opiates; phencyclidine; tetrohydrocannibinol). The drugs of abuse urine screen is performed once at Visit 1; the other laboratory tests are performed at Visit 1, Visit 6 and Visit 7.

⁵ Blood samples for pharmacodynamics including C4 and a lipid panel of total cholesterol, HDL, LDL and triglycerides are obtained at Visits 1, 4 and 7.

⁶Females of child bearing potential are required to have a negative pregnancy test result within 48 hours prior to the receipt of radiation. Females who are status post-tubal ligation, post-hysterectomy or post-menopause are exempted from this requirement

⁷ A six question survey concerning constipation symptoms and treatment efficacy will be given at Visit 3, the end of the pre-treatment period, and again at Visit 6, the end of the treatment period.

⁸An abbreviated transit scintigraphy with scans obtained at 4 and 24h is performed at Visit 2. A full transit with scans obtained at 0, 30 min, 60 min, 90 min, 2, 3, 4, 5, 6, 7 and 8 hours after taking study medication for 12 consecutive days at Visits 4-6.

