Within 7-14 days of Visit 1, patients will return to Charlton 7 CRU fasting for the previous eight hours, no food or drink allowed. Vital signs (pulse, blood pressure, respiration rate and temperature) will be measured. They will be given a capsule containing a small amount of In¹¹¹ radioactivity and asked not to eat anything for the next two hours and to return four hours later for one five minute camera picture. Patients will return the following morning at the same time the capsule was taken for one final five minute camera image. If the camera indicates a state of constipation by showing a geometric center at 24 hours to be less than 2.30, , the median of normal colonic transit in normal healthy volunteers (as determined by analysis of a compilation of prior [name] studies ,the patient will continue in the study and be randomized to the study medication. If the camera does not indicate a state of constipation by showing a geometric center equal to or greater than 2.30, the patient will end the study at this time.

Visit 3 Randomization and Administration of Study Medication

The patient will complete a six question survey of constipation symptoms and treatment efficacy at the end of the pre-treatment period, before receiving study medication. The patient will then be randomized to a dose of the study medication which is either a placebo (an inactive substance) or a 15 mg or 20 mg dose of A3309 study medication taken orally once daily for a total of fourteen consecutive days, eleven doses at home and three at the Charlton CRU during the final transit scintigraphy test, Visit 4 to Visit 6. Patients will dose at home and record the dosing of study medication in their Bowel Pattern Diaries.

Prior to Visit 4

Females of child bearing potential must have a negative urine pregnancy test performed within forty-eight hours prior to receipt of radiation in the abbreviated transit scintigraphy test. Females who have experienced a bilateral tubal ligation, hysterectomy or menopause will not need the pregnancy test.

Visit 4 Final Transit Scintigraphy and Pharmacokinetic Sampling

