12.2 Anticipated results and significance

We anticipate decreased colonic transit without significant effects upon stomach and small bowel transit. We expect no serious adverse events, though the efficacy of the medication being relief of constipation may result in diarrhea, gas and bloating. We also expect a minor decrease in LDL cholesterol and a slight increase in C4, also consistent with the pharmacologic actions of the medication.

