34.6 Survey of Constipation Symptoms and Treatment Efficacy

1.	On average, h	ow would yo	u rate your	constipation	during the past	7 days?
----	---------------	-------------	-------------	--------------	-----------------	---------

- 1 = None
- 2 = Mild
- 3 = Moderate
- 4 = Severe
- 5 = Very severe
- 2. Compared to before you started this study, how would you rate your constipation during the past 7 days?
 - 1 = Completely relieved
 - 2 = Considerably relieved
 - 3 = Somewhat relieved
 - 4 = Unchanged
 - 5 =Somewhat worse
 - 6 = Considerably worse
 - 7 = As bad as I can imagine
- 3. Compared to before you started this study, how would you rate the treatment effectiveness during the past 7 days?
 - 1 = Not at all effective
 - 2 = A little bit effective
 - 3 = Moderately effective
 - 4 =Quite a bit effective
 - 5 = Extremely effective
- 4. How would you rate your abdominal discomfort over the last 24 hours?
 - 1 = None
 - 2 = Mild
 - 3 = Moderate
 - 4 = Severe
 - 5 = Very severe
- 5. How would you rate your abdominal pain over the last 24 hours?
 - 1 = None
 - 2 = Mild
 - 3 = Moderate
 - 4 = Severe
 - 5 = Very severe
- 6. How would you rate your bloating over the last 24 hours?
 - 1 = None
 - 2 = Mild
 - 3 = Moderate
 - 4 = Severe
 - 5 = Very severe

Data and Safety Monitoring Plan

Mayo Clinic CTSA – Research Resources

Protocol Application - Data and Safety Monitoring Plan Template (DSMP)

IRB #: 09-00618 **PI:** [name], MD

Protocol Title: Effects of A3309, an Ileal Bile Acid Transport Inhibitor, on Small Bowel and Colonic

Motor Functions in Female Patients with Functional Constipation

Person Completing This Form: [name], MS Date of Completion/Revision: 10/20/2009

Introduction

Please use the following template to develop or reflect your Data and Safety Monitoring Plan (DSMP). All protocols conducted on the Clinical Research Unit (CRU) or use any CTSA – Research Resources are required to have a DSMP.

Please include the DSMP with your protocol submission to the CTSA – Research Resources. The DSMP also requires IRB approval and may be submitted to the IRB with your new protocol at the time of submission or to the appropriate IRB review board with a modification form if the protocol is already IRB approved.

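### Section 24.6 analyses the constipation survey from post-treatment answers only, leaving the pre-dose answers to questions 1 and 4–6 unused and stating no use of the items' order

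*Combined protocol and SAP*

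**What the plan says.** Three parts of the protocol bear on the survey.

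**Collection.** Footnote 7 to the schedule in 11.2 states: "A six question survey concerning constipation symptoms and treatment efficacy will be given at Visit 3", and again at Visit 6. Section 11.3 places the Visit 3 survey "at the end of the pre-treatment period, before receiving study medication". Appendix 34.6 shows ordered answers throughout: five levels for questions 1 and 3–6, seven for question 2. Questions 1 and 4–6 rate current severity (constipation, discomfort, pain, bloating). Questions 2 and 3 look back to before the study; question 2 reads "Compared to before you started this study, how would you rate your constipation during the past 7 days".

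**Endpoint.** Item 5 in 9.3 rests on a "six question survey given at the end of the pre-treatment period and the post-treatment period". The version in 24.4 is worded differently: "treatment effects on symptom responses specific to constipation, overall and for active treatment compared to placebo". It does not mention the pre-treatment survey.

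**Analysis.** Section 24.6 states that "treatment effects on specific constipation symptoms, considered as discrete categorical responses, will be evaluated by a contingency table analysis of the post-treatment responses". It names no test. The same paragraph analyses stool frequency and consistency by ANCOVA "using the corresponding run-in values as covariates". Section 24.1 and the synopsis apply ANCOVA, including ANCOVA on ranks, to transit parameters and diary summaries. The covariates listed there are age, BMI and baseline diary summaries. Dunnett's test follows an ANCOVA overall p of 0.10 or less. No survey score appears in either place.

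**The concern.** The plan collects a pre-dose answer to four severity questions, names that time point in the endpoint, and then states no analysis that uses it. Two other outcomes in the same paragraph are adjusted for their run-in values. Treating ordered answers as discrete categories also suggests a test that looks for any difference between arms rather than a shift towards milder symptoms. With 36 patients, both choices can cost power.

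Section 24.4 asks for active treatment against placebo, but the only dose-versus-placebo rule, in 24.1, is tied to an ANCOVA that the survey does not receive.

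At stake is the precision of the patient-reported part of secondary endpoint 5. The primary endpoint, colonic geometric center at 24 h, is not involved.

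**Working it through.** **Plan's own figure.** There is none for the survey. The power figures in 24.9 concern transit only.

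**Step 1: what needs no assumption.** Inputs: 3 arms of 12, 36 in total (synopsis), and the answer levels in 34.6.

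- Expected cell count = 12 × (category total) / 36. A value of 5 needs a category total of 5 × 36 / 12 = 15. Three such categories would need 45 answers, so at most two can qualify.
- At least (5 − 2) × 3 = 9 of 15 cells (five-level questions) and (7 − 2) × 3 = 15 of 21 cells (question 2) therefore have expected counts below 5, whatever the data.
- An unordered test spreads over (3 − 1)(5 − 1) = 8 or (3 − 1)(7 − 1) = 12 degrees of freedom. A location test that uses the order has 2.

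The sparse cells point to an exact test rather than the large-sample chi-square. They do not make a contingency table invalid.

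**Step 2: illustrative power.** All of the following are assumptions. Each patient has a latent normal score before and after treatment with correlation r from 0.1 to 0.5. Post = r × pre + √(1 − r²) × noise − treatment shift. Both doses act alike, and the scores are cut into five levels at −1.5, −0.6, 0.5 and 1.4. There were 4,000 trials per scenario, each test at 0.05. Monte Carlo error is √(0.5 × 0.5 / 4,000) = 0.8 points at 50% power. Exact means a permutation chi-square. The last column spans this and two other assumed five-level distributions.

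| Scenario | Pearson % | Exact % | Kruskal-Wallis % | Rank ANCOVA % | Rank ANCOVA − exact, points |
|---|---|---|---|---|---|
| All shift 0.8 SD | 18 | 21–23 | 41–42 | 42–51 | +14 to +29 |
| All shift 1.2 SD | 42–44 | 47–50 | 76–78 | 79–85 | +19 to +39 |
| Half shift 2.4 SD | 28–30 | 33–34 | 49–50 | 50–54 | +8 to +26 |
| Half move to no symptom | 42–44 | 49 | 57–58 | 58–61 | +5 to +12 |
| 45% improve 2.5 SD, 25% worsen 1.2 SD | 28–29 | 31–32 | 18 | 19–20 | −5 to −13 |

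Type I error was 2.6–3.7% (Pearson), 4.8–5.2% (exact), 4.6–5.0% (Kruskal-Wallis) and 5.0–5.6% (rank ANCOVA).

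**Step 3: splitting the gain.** In the most favourable main-set case (1.2 SD, r = 0.5), power is 46.5% exact, 75.9% Kruskal-Wallis and 85.0% rank ANCOVA. The gain of 85.0 − 46.5 = 38.5 points divides into 75.9 − 46.5 = 29.4 from using the order and 85.0 − 75.9 = 9.1 from the Visit 3 score. The baseline part falls to 2.8 points at r = 0.3 and 0.6 at r = 0.1. Against an ordinal table test (row mean scores or Kruskal-Wallis), rank ANCOVA differs by about −2 to +10 points over all scenarios.

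**Step 4: seven-level question 2, no baseline.** Exact against Kruskal-Wallis: 17–18% and 40–42% at 0.8 SD; 41% and 77–80% at 1.2 SD; 30% and 50–51% if half respond; 27–28% and 19% in the mixed case.

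**Cross-check.** A separate permutation simulation assumed a pre-treatment distribution of 2/13/40/33/12% and r from 0.3 to 0.7. For unordered, ordered, and ordered with baseline it gave about 22–23%, 38–42% and 44–60% at 0.8 SD, and about 48%, 78–79% and 78–93% at 1.2 SD.

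**The case against.** The strongest reply has four parts.

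- **Post-treatment comparison is legitimate.** Randomisation makes it unbiased, and 24.4 asks for treatment effects on symptom responses, not change from baseline. This stands. The point is about efficiency, and about 9.3 naming a time point that the analysis leaves out.
- **A contingency table need not be unordered.** A row-mean-score or similar ordinal test fits the words of 24.6. This stands too. A reader might infer that the plan commits to an unordered test and so forgoes up to 39 points, but the text does not say so. On the ordinal reading the difference is small, and the baseline may add almost nothing if r is low.
- **Rank methods can lose.** Section 12.2 expects that "the efficacy of the medication being relief of constipation may result in diarrhea, gas and bloating", so opposite movements are plausible for discomfort, pain and bloating, which are three of the four questions that would receive rank ANCOVA. In the mixed scenario the unordered exact test does better. Tabulating counts makes such movements visible but does not restore the power.
- **A SAP may say more.** The synopsis sends exploratory efficacy analyses to a SAP, and the supplied text contains no separate SAP section on the survey. A reader might also infer that the unnamed test could be picked to suit the results. The documents do not support that: 20.1 keeps the statistician blinded until the analysis data set is final, and a SAP could fix the test first.

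The sentence in 24.6 also covers symptom responses from the diary. This point does not extend to them.

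**Conclusion.** The point holds as a minor one. On the supplied text, 24.6 makes no use of the pre-dose answers to questions 1 and 4–6 and states no use of the order of any of the six questions, while 9.3 names both survey times and the same paragraph adjusts two other outcomes for run-in values.

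A reader might infer that the symptom results would be biased or the trial's main conclusion weakened; neither follows. The consequence is lower precision on part of one secondary endpoint. How much is lost depends on two things that the documents do not settle: which table test is meant, and how patients respond. The loss is large for an unordered test with most treated patients shifting the same way, smaller if only some respond, slight for an ordinal test, and reversed if treatment moves patients in both directions. All power figures rest on assumed effects, distributions and correlations. Only the cell-count and degrees-of-freedom results are free of those assumptions.

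**What to change.** Amend 24.6, with matching wording in 24.1 and the synopsis (add the Visit 3 survey scores to the covariate list, and extend ANCOVA on ranks and the p ≤ 0.10 rule to the survey):

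1. Questions 1 and 4–6: ANCOVA on ranks with the Visit 3 score as covariate.
2. Questions 2 and 3, which have no usable baseline: Kruskal-Wallis.
3. Each dose against placebo: keep the overall p ≤ 0.10 rule, followed by Dunnett on ranks for questions 1 and 4–6 and Steel's many-to-one rank test for questions 2 and 3.
4. For all six questions, still tabulate category counts by arm so that opposite movements remain visible.

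Under the same kind of assumptions, step 3 kept familywise error at 5.0–5.3% for the Dunnett route (critical value 2.31 on 36 − 3 − 1 = 32 degrees of freedom), with 68–76% power per dose at 1.2 SD. The Steel route (critical value 2.21) gave 4.5–4.9% and 65–67%.

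The cost is wording only: no new data and no extra visit. The downside is the 5 to 13 points lost against an unordered exact test if treatment helps some patients and worsens others.
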